8.3.3 Ventilation protocol in INTELLiVENT-ASV ventilation group

Subject allocated to INTELLiVENT-ASV group will be ventilated with this mode from inclusion to the end of the study. Tube resistance compensation (TRC) can be added.

A. Passive subjects:

i. Ventilator settings:

Clinician will set the IBW, subject condition, PetCO₂ and SpO₂ targets, PEEP ranges, and alarms and activate the controllers. The minimal FiO₂ will be set at 0.21. An arterial blood gas will be performed 30-60 min later in order to adjust the PetCO₂ target.

Table 3: Management of pH and PaCO₂:

pH < 7.15	pH= 7.15 – 7.29	pH= 7.29 – 7.45	pH > 7.45
Decrease PetCO ₂ targets by 5 mm Hg and keep PaCO ₂ > 25 mm Hg	Decrease PetCO ₂ targets by 5 mm Hg and keep PaCO ₂ > 25 mm Hg	No change	Increase PetCO ₂ targets by 5 mm Hg
Consider NaHCO ₃	Consider NaHCO ₃		

ii. Controller deactivation

PEEP and FiO₂ controller will be transiently deactivated if it is not possible to get a good SpO₂ signal with both finger and ear sensors. SpO₂ signal quality will then be re-assessed every 6h in order to restart oxygenation controller as soon as possible.

PEEP controller is by design deactivated when brain injury and chronic hypercapnia conditions are selected. PEEP will be set manually as in the non-automated ventilation group.

PEEP controller will not be deactivated in normal and ARDS conditions. Clinician can adjust PEEP ranges and use very narrow ranges if it is clinically needed.

Ventilation controller will be de-activated only if the clinical condition needs a %MV below 70% or above 200%.

Reasons and duration of controllers de-activation will be recorded in the eCRF.

B. Spontaneous breathing subjects:

i. Ventilator settings:

Clinician will set the IBW, subject condition, PetCO₂ and SpO₂ targets, PEEP ranges, and alarms and activate the controllers. The minimal FiO₂ will be set at 0.21. An arterial blood gas will be performed 30-60 min later in order to adjust the PetCO₂ target.

PEEP will be kept in the range:

- 5-10 cmH₂O for normal lung subjects and COPD
- 5-15 cmH₂O for ARDS and obese subjects

C. Weaning:

Weaning in the INTELLiVENT-ASV group will use quick wean function.

i. Quick wean activation

Quick wean will be activated when subject is stabilized with absence or minimum doses of sedation and vasopressor.

If subject has a coma Glasgow score above 8, quick wean function will be activated with SBT.

If subject has a coma Glasgow score below or equal to 8, quick wean function will be activated without SBT initially and SBT will be activated when the coma Glasgow score is above 8.

ii. Quick wean settings

Observation time will be set at 30 min before starting SBT.

Period between 2 SBT will be adjusted by the clinician according to the clinical needs.

Default settings to start SBT will be used:

PEEP \leq 8 cmH₂O

FiO₂ \leq 40%

Tolerance time: 180 s

RR \leq 35 b/min

Minimum VT \geq 5 mL/kg IBW

Rapid Shallow Breathing index \leq 105

PS between 5 and 12 cmH₂O

iii. Weaning trial

Weaning trial will use the automatic SBT of the quick wean option with a PEEP of 5 cmH₂O, a %MV at 25%, and a duration of 30 min.

Criteria to abort SBT will be:

- PEEP $>$ 8 cmH₂O for the duration of tolerance time
- FiO₂ $>$ 50% for the duration of tolerance time
- Tolerance time: 180 s
- RR $>$ 35 b/min for the duration of tolerance time
- Minimum VT $<$ 5 mL/kg IBW for the duration of tolerance time
- Rapid Shallow Breathing index $>$ 105 for the duration of tolerance time
- PS $>$ 12 cmH₂O
- RR increase $>$ 50%
- PetCO₂ increase $>$ 8 mm Hg
- Apnea defined by a spontaneous RR below the target RR determined by ASV controller
- SpO₂ sensor failure

iv. Extubation

After a failed SBT, the clinician may decide to repeat it the same day or to stop SBT for some time, keeping the quick wean function active.

After a successful SBT, clinician will check the extubation criteria. If all criteria are fulfilled, extubation will be performed within 12 h.

8.3.4 Measurements

Breath-by-breath ventilation variable will be recorded during the full duration of study period.

On top of that, ΔP , P_{plat} , total PEEP, and blood gas results (if performed) will be measured twice a day and reported on the eCRF.

Information of acute pulmonary condition will be recorded in the eCRF.

Information about controllers de-activation and weaning process will be reported on a daily basis on the eCRF.

All concomitant medications will be recorded in the eCRF including sedation.

8.4 End of study (extubation + 48 hours):

The end of study visit should be completed at the time a subject completes the study ventilation protocol. It means that the subject is extubated and there is no need for re-intubation within 48 hours.

Subject reintubated within 48h after extubation will continue to be ventilated per the allocated randomized ventilation mode.

Subject re-intubated beyond 48h will be considered as weaned for the ventilation procedure. They remain in the study but only a phone call will be done on Day 28.

Following data point to be collected and recorded:

- Intubation/ re-intubation status
- Acute Pulmonary Condition
- Vital Signs
- Ventilator parameters manual assessment
- 24h Recording of ventilation parameters (Memory Box)
- Blood gas analysis (If available visit $\pm 2h$)
- SOFA score
- Concomitant sedation, analgesia and myorelaxants use
- Concomitant vasopressors and inotropics use
- Number of recruitment maneuvers within the last observation period
- Concomitant rescue therapies (proning, Nitric oxide, ...)
- Weaning information associated interventions (Patient Passive/Active but still on MV, NIV, CPAP, High Flow.)
- Screening of readiness to extubate criteria (SBT)
- Assessment of re-intubation status

- Extubation failure
- Acute Kidney Injury (AKI) status and need for RRT
- Critical illness polyneuro- myopathy status
- Critical illness encephalopathy status
- Tracheostomy status
- Resuscitated cardiac arrest status
- Other imminently life-threatening experience
- Barotrauma status
- Rescue therapy requirement (APRV, high frequency ventilation, ECCO₂R and ECMO).
- Withhold of weaning and/or withdrawal of mechanical ventilation status
- Ventilation duration for study period (if reintubated beyond 48h)
- ICU and hospital length of stay
- ICU mortality (if subjects hospitalized somewhere else) or 28 Days mortality
- Adverse Event collection

8.5 Study Exit (Day 28):

Prior to completion of study close out, all subject data must be captured and monitored in the eCRF.

A subject will be considered to have completed the study for the following reasons:

- Subject completes follow-ups (Day 28) required per investigational plan.
- Subject dies.
- Subject or legally authorized representative requests to be withdrawn from the study.
- Investigator requests to be withdrawn from the study to protect the welfare of the subject. (In that case, it is at the site's principal investigator's discretion to determine that the study is no longer in the subject's best interest.)

In case of sponsor's decision to stop the study, the site will be notified by the sponsor in written of the intention to close the study. Study close out visits are then to be performed. During these visits, the monitors will ensure that the investigator's regulatory files are up to date and complete and that any outstanding issues from previous visits have been resolved. The site will be informed that all requirements have been met with a study closure letter.

Following data point to be collected and recorded:

- Intubation status
- Acute Pulmonary condition
- Extubation failure - with SBT
- Acute Kidney Injury (AKI) status and need for RRT

- Critical illness polyneuro- myopathy status
- Critical illness encephalopathy status
- Tracheostomy status
- Ventilation duration for study period (if reintubated beyond 48h)
- ICU and hospital length of stay
- ICU mortality
- Adverse Event collection

8.6 Supply and Accountability

Ventilation system serial number utilized for each subject will be documented and placed in the subject's study file.

8.7 Ancillary Supplies

Additional equipment or consumables such as heated humidifier, ventilator circuit, flow sensor, SPO₂ sensor and CO₂ sensor cupula will be supplied by Hamilton Medical, if needed. The ancillary supplies have all market authorization in US and European country sites.

9 SAFETY

Please refer to:

Annex A

Identification of Risks and Adverse Events (AE's) for the intended subject population, the clinical background and the device in question identified from clinical experience for INTELLiVENT-ASV

Annex D: List of Adverse Event

List of reportable Adverse Event

9.1 Recording and reporting of AEs

- **Recording:** Entry of an event into the clinical database by site staff as they “become aware” (Soladis System) or into the safety database by the safety team (VigOps). .
- **Reporting:** Sending a report to the National Competent Authority, EC/IRB. Sites are responsible for submitting reports to their IRB or EC in most countries.

The EASiVENT study includes a general ICU patient population in need of mechanical ventilation for at least 24 hours. This population includes critically ill patients spanning a variety of primary and secondary medical conditions that can cause AEs including severe disability and death irrespective of study participation. The expected mortality in EASiVENT Study patient population is around 30%.

Given the high acuity of diseases and morbidity related to ICU patient populations, not all AEs will be reported in the EASiVENT Study.

AE information will be collected throughout the study and reported to Hamilton Medical on the Adverse Event collected in the eCRF. The investigator is responsible for detecting, documenting and reporting AEs to Hamilton Medical through the eCRF or via a paper form if the eCRF is not available.

For AEs that require immediate reporting (see Table 4: Adverse Event Reporting Requirements), initial reporting may be done using the Events Form via email to VCLS VigOps (contact details will be provided in the investigational site file), or in the Serious Adverse Events form in the eCRF with as much information as is available. In case the investigator requires information from the Sponsor in an emergency situation, the contact details for emergency situations are given in the investigational site file.

Investigators in the US should submit Unanticipated Device Effects (UADEs) to their IRBs at the same time as notifying VCLS VigOps.

9.1.1 Study-Specific Clinical Outcomes

A list of anticipated AEs (AAEs) that are expected from underlying disease states are listed in Annex A of protocol – “*Clinical manifestations and medical occurrences, unintended diseases or injuries or clinical signs that are attributed to the concurrent illness / clinical condition of critically ill subjects in an ICU include*”.

All AEs that are listed under the above mentioned section of Annex A will be classified as “*study-specific clinical outcomes*”, as these AE(s) are by their nature, incidence, severity, and outcome previously identified in the risk analysis report and the State-of-the-Art analysis.

Study-specific clinical outcomes of patients in need of mechanical ventilation will be recorded in eCRF as secondary outcomes and **will not be recorded** as AEs **unless** the investigator deems the AE to be possibly, probably or definitely (causal) related to the mechanical ventilation itself (or lead to permanent discontinuation of study interventions (except death events that are considered as study specific clinical outcomes)), in which case such events would be recorded as (AEs).

The following AE(s) will be considered study-specific clinical outcomes:

1. Death related to the underlying illness or associated conditions based on the interpretation of the investigator.
2. Significant hemodynamic instability, defined as (a) norepinephrine-equivalent vasopressor dose initiation or increase from any dose that is both double and at least 0.15 mcg/kg/min increased over ≤ 60 minutes to maintain blood pressure target OR (b) dobutamine-equivalent inotropic dose initiation or increase from any dose that is both double and at least 5 mcg/kg/min over ≤ 60 minutes to maintain cardiac output target in case of left or right ventricular dysfunction/failure) that is related to the underlying illness or associated conditions based on the interpretation of the investigator
3. Progression of respiratory failure as demonstrated by new post-enrollment use of respiratory rescue therapy (e.g. ECMO, ECCO₂R, inhaled vasodilators, prone positioning), that is related to progression of the underling illness or associated conditions based on the interpretation of the investigator.
4. Anoxic brain injury that is related to the underling illness or associated conditions based on the interpretation of the investigator
5. Extubation failure that is related to progression of the underling illness or associated conditions based on the interpretation of the investigator.
6. Need for tracheostomy that is related to progression of the underling illness or associated conditions based on the interpretation of the investigator.

9.1.2 Adverse Events (AEs)

ISO 14155 / MDR 2017/745 Definition (regulatory definition):

An AE is any untoward medical occurrence, unintended disease or injury or any untoward clinical signs, (including an abnormal laboratory finding,) in subjects, users or other persons, in the context of a clinica investigation, whether or not related to the investigational medical device. and whether anticipated or unanticipated.

NOTE 1 to entry: This definition includes events related to the investigational medical device or the comparator.

NOTE 2 to entry: This definition includes events related to the procedures involved.

NOTE 3 to entry: For users or other persons, this definition is restricted to events related to investigational medical devices.

Specificities to EASiVENT:

The following Adverse Events (**AEs**) **will be recorded during** the EASiVENT Study Days 0 through 28:

1. Serious Adverse Events (SAEs) other than those listed as study-specific outcomes
2. Non-serious AEs that are considered by the investigator to be possibly, probably, or definitely (causally) related to mechanical ventilation as a supportive measure for acute respiratory failure.
For details please refer to EASiVENT Study list of Adverse Event, [Annex D](#)
3. AEs that lead to permanent discontinuation of INTELLiVENT-ASV-Management.

Investigators will be instructed to record their assessment of the potential relatedness of each Adverse Event (AE) to protocol procedures and mechanical ventilation. Potential relatedness of an event to mechanical ventilation will be determined by evaluating the temporal relationship and if the event is unanticipated or unexplained given the patient's clinical course, care, and previous medical conditions. The degree of certainty the investigator has regarding relatedness of the event to mechanical ventilation will be recorded as not related, possibly related, probably related, or definitely (causal) related. If patient's INTELLiVENT-ASV-Management is discontinued as a result of an AE, study site personnel will clearly record in the eCRF of the Study the circumstances and data leading to discontinuation of INTELLiVENT-ASV as ventilation mode.

By the nature of this patient population a myriad of **non-serious Adverse Events (AEs)** will occur during the Study. Due to the complexity of critical illness, it may be difficult for the investigators to classify whether an Adverse Event (AE) is related or not to the underlying condition or the sequelae of it or to mechanical ventilator support.

Therefore, investigators will be instructed that events such as:

- a. transitory hypertension or
- b. hypotension, tachy- or bradycardia,
- c. arrhythmias (such as atrial fibrillation, heart block, ventricular tachycardia, or ventricular fibrillation),
- d. transitory hypoxemia or
- e. hypercapnia,
- f. impaired cognitive function due to sedation/analgesia or delirium (see AE list attached),

Are not considered study population specific clinical outcomes and **should be recorded** as adverse events **only** if they are **serious** events **or are considered to be related to mechanical ventilation or lead to discontinuation of INTELLiVENT-ASV mode.**

The blinded medical monitor and DSMB will evaluate investigator-reported SAEs and AEs and independently assess potential relatedness to study procedures and, where indicated, make recommendations for safety modifications to the protocol, temporary suspension, or even termination of the study.

9.1.3 Serious Adverse Event (SAE)

ISO 14155 / MDR 2017/745 Definition (regulatory definition):

An SAE is any adverse event that led to any of the following:

- a) *led to a death*
- b) *led to a serious deterioration in health of the subject, users or other persons as defined by one or more of that resulted in any of the following:*
 - *a life-threatening illness or injury, or*
 - *a permanent impairment of a body structure or a body function, including chronic diseases, or*
 - *in-subject hospitalization or prolongation of existing patient hospitalization, or*
 - *in medical or surgical intervention to prevent life threatening illness or injury or permanent impairment to a body structure or a body function,*
 - *Chronic disease,*
 - *led to foetal distress, foetal death or a congenital abnormality or birth defect including physical or mental impairment physical or mental impairment or birth defect.*

Specificities to EASiVENT:

SAE recording begins after the patient has signed informed consent and has received INTELLiVENT-ASV or standard of care mechanical ventilation (point of enrollment). If a patient experiences a SAE after signing informed consent, but prior to receiving the study intervention, the event will not be recorded unless the investigator feels the event may have been caused by a study procedure.

SAEs will be collected Day 0 through Day 28 of the study period or until extubation, whichever occurs first. Thereafter, SAEs are not required to be recorded unless the investigator feels the events were possibly, probably, or definitely (causal) related to study procedures.

An SAE is any Adverse Event (AE) that results in one of the following events and is not classified as a study-specific clinical outcome using the definitions enumerated above:

1. Death that is not related to the underlying illness or associated condition or death that is possibly, probably, or definitely (causal) related to study procedures
2. Resuscitated cardiac arrest that is not related to the underlying illness or associated condition, or that is possibly, probably, or definitely (causal) related to study procedures
3. Significant hemodynamic instability defined as (a) norepinephrine-equivalent vasopressor dose initiation or increase from any dose that is both double and at least 0.15 mcg/kg/min increased over > 60 minutes to maintain blood pressure target OR (b) dobutamin-equivalent inotropic dose initiation or increase from any dose that is both double and at least 5 mcg/kg/min over > 60 minutes to maintain cardiac output target in case of right ventricular dysfunction/failure, that is not related to the underlying illness or associated condition or that is possibly, probably, or definitely (causal) related to study procedures

4. Gross barotrauma (pneumothorax, pneumomediastinum, or subcutaneous emphysema) requiring chest tube or other surgical intervention, where the apparent barotrauma is not related to a procedural complication (e.g., a central venous catheter insertion causing pleural injury)
5. Significant hypercapnic acidemia ($\text{PaCO}_2 > 60 \text{ mm Hg}$ and $\text{pH} < 7.20$ with $\text{Vt} > 8 \text{ ml/kg PBW}$ and $\text{RR} > 30 \text{ b/min}$) for at least two consecutive arterial blood gas measurements 60 min apart
6. Significant hypocapnic alkalemia ($\text{PaCO}_2 < 30 \text{ mm Hg}$ with $\text{pH} > 7.50$) for at least two consecutive arterial blood gas 60 min apart
7. Significant hypoxemia (oxygen saturation < 85% or $\text{PaO}_2 < 55 \text{ mm Hg}$ with $\text{FiO}_2 1.0$) sustained for at least 30 minutes for at least two consecutive arterial blood gas measurements 60 min apart
8. Progression of respiratory failure as demonstrated by new post-enrollment use of respiratory rescue therapy (e.g. ECMO and ECCO₂R), if it is considered as related (possibly, probably, definitely (causal)) to the ventilation mode and neither to the underlying illness nor associated conditions based on the interpretation of the investigator.
9. Hypoxic brain injury, which must be documented with a confirmatory neuroimaging and other clinical evaluations as per local routine practice as applicable, a documented significant hypoxemia event (defined above) during study participation, that is not related to the underlying illness or associated condition
10. Other imminently life-threatening event that is not related to the underlying illness or associated condition or that is possibly, probably, or definitely (causal) related to study procedures
11. Site investigator decides to change the allocated ventilation mode because if it is considered as related (possibly, probably, definitely (causal)) to the ventilation mode and neither to the underlying illness nor associated conditions based on the interpretation of the investigator.

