A period of assisted breathing lasting less than 24 hours and for the purpose of a surgical procedure will not count against the VFD calculation.

If a subject was receiving assisted invasive breathing on day 27 or dies prior to day 28, VFDs will be - 1.

For subjects transferred to another hospital or other health care facility, study data collection will be stopped but subject will be contacted via a phone call on day 28 post enrollment to assess VFD endpoint if possible:

- ICU and hospital length of stay (discharge).

- ICU mortality (if the subjects is hospitalized in another hospital than the investigational site)
- Non-intensive ventilation (NIV) duration
- 28 days mortality
- Ventilation duration for study period (if reintubated beyond 48h)

Dropout could occur when patients are ventilated for less than 24 hours after inclusion because of unexpected death, transfer to another ICU, or withdrawal of informed consent. A maximum dropout rate of 5% of these cases is expected.

Associated interventions:

1. Duration and doses of sedative infusion
2. Duration and doses of analgesic infusion
3. Duration and doses of vasopressors
4. Duration and doses of myorelaxant
5. Number of recruitment maneuvers
6. Time spent in prone position
7. Time spent with nitric oxide

Workload:

1. Number of manual adjustment will be collected in both ventilation arms until considered as weaned from the ventilation.

Safety:

The secondary safety endpoint will be determined by evaluating the number of Serious Adverse Events (all SAEs included) within 28 days of the enrollment and the rescue therapy requirement (APRV, high frequency ventilation, ECCO2R and ECMO).

In addition to better characterise the risk profile of the study population the following non-mechanical ventilation related adverse events will be recorded on study day 7 and 28.

- Severe Acute kidney injury (AKI) in need for CRRT/IHD
- Severe critical illness neuro-myopathy signs of tetraplegia affecting arms shoulder and neck with potential implication of respiratory muscle. Weakness is documented using the following score points: score 0 for no visible muscle contraction, score 1 for visible muscle contraction with no or trace movement, score 2 for limb movement, but not against gravity and score 3 for movement against gravity but not resistance.

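### Protocol 9.1.3 stops routine SAE recording at extubation, which contradicts 9.1.2, the Day 28 schedule and the 28-day SAE endpoint

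*Protocol*

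**What the plan says.** Protocol 9.1.3 sets the SAE window: "SAEs will be collected Day 0 through Day 28 of the study period or until extubation, whichever occurs first". The next sentence says that from then on "SAEs are not required to be recorded unless the investigator feels the events were possibly, probably, or definitely (causal) related to study procedures". The same section gives a trial-specific definition, "An SAE is any Adverse Event (AE) that results in one of the following events and is not classified as a study-specific clinical outcome", followed by 11 listed events.

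Protocol 9.1.2 sets a different window. Among the events to be recorded during "the EASiVENT Study Days 0 through 28" it lists "Serious Adverse Events (SAEs) other than those listed as study-specific outcomes". It has no stop at extubation and no relatedness condition for these.

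The secondary safety endpoint in Protocol 5.2 is the "number of Serious Adverse Events (all SAEs included) within 28 days of the enrollment", together with the need for rescue therapy. The Protocol synopsis, SAP 3.2.2 and SAP 8.3 repeat it. Protocol 9.1 has adverse event information collected for the whole study. Protocol 8.5 and the assessment schedules (Protocol Table 1, SAP Appendix 1) list adverse event collection at Day 28. SAP 4.9 names only the site inclusion cap as a change to the protocol, so nothing reconciles the two windows.

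**The concern.** A site cannot tell which rule governs. For an unrelated listed SAE on, say, Day 15 in a subject extubated on Day 6, 9.1.2 requires an entry and 9.1.3 does not. The recorded count would then depend partly on which section each site follows, and the SAP counts SAEs without mentioning the cut-off.

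The cut-off is also a post-randomisation event that the intervention may affect. Protocol 8.3.3 has the INTELLiVENT-ASV arm wean with Quick Wean, while 8.3.2 gives the control arm other weaning trials. If time to extubation differs, the two arms' counts cover unequal windows. After extubation the duty to record rests on a relatedness judgement by staff who know the allocation (Protocol 6.2.2). The synopsis says that the results feed a pre-market benefit-risk determination, so the SAE count should mean what the endpoint says.

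**Working it through.** No figure in the plan depends on this rule, so there is nothing to reproduce. The check is a comparison of the texts, then a bound on which events are affected, then an illustration on assumed inputs.

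**1. The windows side by side**

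| Place | Window | Condition after extubation |
|---|---|---|
| Protocol 9.1.2 | Days 0 to 28 | none (study-specific outcomes excluded) |
| Protocol 9.1.3 | to extubation or Day 28, whichever is earlier | only if felt related to study procedures |
| Protocol 5.2, SAP 3.2.2 and 8.3 | 28 days from enrolment | none |
| Protocol 8.5, schedules | Day 28 adverse event collection | none |

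Section 9.1.3 is the outlier. For an extubated subject its rule cannot supply the endpoint.

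**2. Which listed events are exposed**

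- Items 8 and 11 need a link to the ventilation mode. Item 8 applies "if it is considered as related (possibly, probably, definitely (causal)) to the ventilation mode and neither to the underlying illness nor associated conditions", and item 11 begins "Site investigator decides to change the allocated ventilation mode because if it is considered as related". Item 5 needs tidal volume and rate criteria. These are essentially on-ventilator events.
- Items 1, 2, 3, 9 and 10 carry an underlying-illness clause. After extubation they go unrecorded only if related neither to the illness nor to study procedures.
- Items 4, 6 and 7 (barotrauma, hypocapnic alkalemia, hypoxemia) have no such clause. However, Annex A lists barotrauma from ventilation during emergency therapies among the conditions that 9.1.1 treats as study-specific outcomes. Items 6 and 7 need two consecutive arterial gases 60 min apart.
- Protocol 8.4 collects barotrauma, resuscitated cardiac arrest and other imminently life-threatening status at extubation + 48 h. Mortality, extubation failure and re-intubation are also collected (Protocol 5.2, 8.4, 8.5).

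What remains is listed SAEs judged unrelated to study procedures, mainly those later than 48 h after extubation.

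**3. Illustration on assumed inputs**

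The documents give no ventilation time by arm and no SAE rate on or off the ventilator. Annex A Table 10 gives 2 to 8 days of ventilation as background, which is 2/28 = 7% to 8/28 = 29% of the window.

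Assumptions: exponential ventilation time with mean m days; listed SAEs after extubation occur at r times the on-ventilator rate; full capture for 48 h after extubation; 20% capture later.

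- On-ventilator days: o = m(1 − exp(−28/m))
- First 48 h after extubation: p = 2 + m(1 − exp(−26/m)) − o
- Later days: l = 28 − o − p
- True count ∝ o + r(p + l); recorded count ∝ o + r(p + 0.2l)

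For m = 8: o = 7.76, p = 1.93, l = 18.31. For m = 6: 5.94, 1.98, 20.08.

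Worked case, r = 0.10:
- m = 8: true 7.76 + 0.10 × 20.24 = 9.78; recorded 7.76 + 0.10 × (1.93 + 3.66) = 8.32; missed 15.0%.
- m = 6: true 5.94 + 0.10 × 22.06 = 8.15; recorded 5.94 + 0.10 × (1.98 + 4.02) = 6.54; missed 19.7%.
- Distortion of the arm ratio: 1 − (0.803/0.850) = 5.6%, in favour of the arm extubated sooner.

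| r | Missed, mean 8 d in both arms | Ratio distortion, 8 vs 7 d | Ratio distortion, 8 vs 6 d |
|---|---|---|---|
| 0.25 | 28.6% | 4.2% | 9.1% |
| 0.10 | 15.0% | 2.5% | 5.6% |
| 0.05 | 8.4% | 1.4% | 3.3% |
| 0.02 | 3.6% | 0.6% | 1.5% |

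With equal means the ratio is not distorted. If 30% of subjects (the expected mortality in Protocol 9.1) die while intubated and are fully covered, the 8 vs 6 column runs from 7.8% down to 1.1%. None of these rows is an estimate for this trial.

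**The case against.** The strongest defence is that restricted event recording is deliberate in this population (Protocol 9.1, 9.1.2) and that other data collection fills most of the gap. Much of that stands. Later SAEs are optional rather than barred, related ones stay mandatory, and step 2 shows that few event types are exposed. It does not remove the conflict, because the endpoint and 9.1.2 were not restricted to match.

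A reader might infer more than the documents support:

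- *That the SAE comparison is biased towards the device by a known amount.* At one constant SAE rate on and off the ventilator, and with nothing captured after extubation, 6 vs 8 ventilation days would give a recorded ratio of 6/8 = 0.75 against a true ratio of 1.0. The listed events are mostly on-ventilator events, so an equal rate is implausible, and no arm difference in ventilation time is documented. The illustration above is equally assumption-bound. In particular, 9.1.3 does not itself provide the 48 h of full capture, and nothing links any r to the list.
- *That harm from too-early extubation, which Annex A names as an anticipated device effect, goes unseen.* Extubation failure and re-intubation are collected regardless, and SAEs judged related remain recordable.
- *That a subject re-intubated within 48 h falls outside collection.* Protocol 5.2 counts that interval as invasive ventilation and uses the last extubation, and 8.3.1 qualifies extubation in the same way. Section 9.1.3 omits this convention, but it exists.
- *That no between-group SAE comparison is planned.* SAP 8.3 plans tabulation only, but SAP 7.2 lists safety events among variables compared by a Z-test or Mann-Whitney test.

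**Conclusion.** The contradiction is certain on the text and should be corrected. A site that follows 9.1.3 cannot deliver the 28-day endpoint, and its count covers a window that ends at an outcome the device may influence. How many events would be lost, and whether the arms would be affected unequally, cannot be determined from the documents. That depends on off-ventilator SAE rates, on arm differences in ventilation time and on site practice, and none of these is given. The primary endpoints are untouched. A separate mismatch belongs to the same correction: the endpoint claims to include every SAE, while 9.1.1 to 9.1.3 exclude study-specific clinical outcomes.

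**What to change.** 1. In Protocol 9.1.3, delete the extubation alternative from the collection sentence, so that SAEs are recorded through Day 28 in both arms. Keep the sentence that follows it. It then applies only after Day 28, and it is the only text asking for related SAEs beyond that day.
2. In the Protocol synopsis, Protocol 5.2, SAP 3.2.2 and SAP 8.3, replace the claim to include every SAE with all SAEs other than study-specific clinical outcomes, to match 9.1.1 and 9.1.2.
3. If the sponsor prefers to keep the cut-off, restate the endpoint in those four places as SAEs up to last extubation, using the existing 48 h re-intubation convention, plus related SAEs to Day 28. Report it with time at risk by arm. SAP 10.1 already plans a table of ventilation exposure.

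The cost is a wording amendment and some extra SAE entry after extubation; the Day 28 contact and adverse event collection already exist. Ascertainment will stay incomplete for transferred subjects, who are telephoned at Day 28 only if possible, and will rest on one call for those re-intubated beyond 48 h.
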